4.5.1. COVID-19 Assessment and COVID-19 AEs

Based on the study requirement, related analysis or a listing will be produced for the study.

A standardized MedDRA Query (SMQ) will be used to identify all COVID-19 AEs.

The overall incidence of COVID-19 AEs and SAEs, COVID-19 AEs leading to study intervention discontinuation, COVID-19 AEs leading to study withdrawal, and severe COVID-19 AEs will be summarized. The incidence of these events at individual PT level can be obtained from the standard AE/SAE summaries.

COVID-19 assessments (confirmed, probable and suspected diagnosis) for participants with COVID-19 AEs will be summarized.

The number and percentage of participants with concomitant vaccination (COVID-19) before and during the study will be tabulated with exact 95% CI.

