Return of diary cards		○	○		See Section 10.3.7 for more information
Recording of solicited events (Days 1-4 after study intervention administration)	●	●	●		See Sections 10.3.3 and 10.3.7 for more information
Recording of unsolicited events (Days 1-30 after study intervention administration)	●	●	●		See Sections 10.3.4 and 10.3.7 for more information
Recording of concomitant medications/vaccinations	●	●	●	●	See Section 6.8 for more information

Type of contact	Visit 1	Visit 2	Visit 3*	Contact	Notes
Timepoints	Day 1	Day 31	Day 61	Month 7 ¹	
Recording of intercurrent medical conditions	•	•	•	•	See Section 9.3.1 for more information
Recording of SAEs and pIMDs	•	•	•	•	See Section 10.3.7 for more information
Recording of AEs/SAEs leading to withdrawal from the study	•	•	•	•	See Section 10.3.7 for more information
Recording of SAEs related to study participation, or to a concurrent GSK medication/vaccine ⁶	•	•	•	•	See Section 10.3.7 for more information
Contact for safety follow-up				•	See Sections 8.2.2 and 10.3.7.2 for more information
Study conclusion				•	See Section 4.4 for more information

Note: The double-line borders indicate analyses which will be performed on all data obtained up to these time points.

• is used to indicate a study procedure that requires documentation in the individual eCRF

○ is used to indicate a study procedure that does not require documentation in the individual eCRF

AE = adverse event; pIMDs = potential-immune-mediated diseases; SAE = Serious Adverse Event; eCRF = electronic Case Report Form.

FLU vaccine = FLU HD quadrivalent.

*Visit 3 should preferably be done on site but if deemed necessary, local regulations allow, and quality of study procedures is maintained, this study visit can be replaced by a home visit conducted by authorized staff. Any information from the participant required according to study procedures and not collected during the home visit, can be obtained by means of a phone call conducted by the site staff.

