4. STUDY DESIGN

4.1. Overall design

Figure 1 Study design overview

1MPD = 1-month post-dose.

* Blood sample only from participants in Control group.

FLU = FLU HD quadrivalent; RSV = RSVPreF3 OA investigational vaccine; BS = Blood sample from all participants (except for blood sample at Visit 3 which is only applicable for Control group).

Note: Unsolicited AEs will be collected from first dose to 30 days post-dose. SAEs and pIMDs will be collected from first dose through the entire study period. SAEs related to study participation will be collected from the time of consent.

- **Type of study:** self-contained.
- **Experimental design:** phase 3, randomized, open-label, multi-country study with 2 parallel groups (see [Figure 1](#)).
- **Duration of the study:** ~ 6 months for participants in Co-Ad group; ~ 7 months for participants in Control group.
- **Primary completion date:** Day 61 (1 month after the RSVPreF3 OA investigational vaccine dose in Control group).
- **Control:** active comparator, i.e. staggered administration of licensed FLU vaccine and RSVPreF3 OA investigational vaccine.
- **Blinding:** open-label. Refer to Section [6.3.5](#) for details.
- **Data collection:** standardized electronic Case Report Form (eCRF). Solicited events and unsolicited AEs will be collected using a participant Diary card (paper Diary card).
- **Safety monitoring:** the study will be conducted with oversight by the project Safety Review Team (SRT). Please refer to Section [10.1.5](#) for the SRT structure.
- **Vaccination schedule:**
 - **Co-Ad group:** Participants will receive a single dose of RSV investigational vaccine and a single dose of FLU vaccine at Visit 1 (Day 1).
 - **Control group:** Participants will receive a single dose of FLU vaccine at Visit 1 (Day 1), followed by a single dose of the RSV investigational vaccine at Visit 2 (Day 31).
- **Study groups:** Refer to [Figure 1](#) and [Table 6](#) for an overview of the study groups.

Table 6 Study groups and intervention

Study groups	Number of participants	Age (Min-Max)	Study interventions
Co-Ad	~514	≥65 years	RSVPreF3 OA investigational vaccine
			FLU HD
Control	~514	≥65 years	RSVPreF3 OA investigational vaccine
			FLU HD

FLU HD = FLU HD quadrivalent

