8.3. Adverse Events (AEs), Serious Adverse Events (SAEs) and other safety reporting

8.3.1. Time period and frequency for collecting AE, SAE and other safety information

Table 12 Timeframes for collecting and reporting of safety information

Co-Ad group		Pre-Dose*	Vacc Co-Ad	6 months post-last dose** Study conclusion		
Event		D1	D4	D31		
Administration site and systemic solicited events						
Unsolicited AEs						
Control group						
	Pre-Dose*	Vacc FLU		Vacc RSV		6 months post-last dose** Study conclusion
	D1	D4	D31	D31	D34	D61
Administration site and systemic solicited events						
Unsolicited AEs						
All participants						
All SAEs						
All pIMDs						
SAEs related to study participation or concurrent GSK medication/ vaccine						
AEs/SAEs leading to withdrawal from the study						
Intercurrent medical conditions						

D: day; AE: adverse event; SAE: serious adverse event; pIMD: potential immune-mediated disease; Vacc: Vaccination.
* i.e. consent obtained on Day 1 (prior to intervention administration).

** post-last dose= 6 months after Co-Ad vaccine administration (Co-Ad group) or 6 months after RSV investigational vaccine administration (Control group).

Note: COVID-19 cases will be collected during the same timeframes as those used for collecting and reporting the other safety information (unsolicited AEs/SAEs, etc.)

The investigator or designee will record and immediately report all SAEs to the sponsor or designee via the Expedited AE Reporting Form. Reporting should, under no circumstances, occur later than 24 hours after the investigator becomes aware of an SAE, as indicated in Section 10.3.9. The investigator will submit any updated SAE data to the sponsor within 24 hours of it being available.

A post-study AE/SAE is defined as any event that occurs outside of the AE/SAE reporting periods defined in [Table 12](#). Investigators are not obligated to actively seek AEs or SAEs from former study participants. However, if the investigator learns of any SAE, including a death, at any time after a participant has been discharged from the study, and he/she considers the event to be reasonably related to the study intervention, the investigator will promptly notify the study contact for reporting SAEs mentioned in the [Table 14](#).

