10.3.7.1. Time period for collecting and recording AEs, SAEs, and pIMDs

All solicited administration site and systemic events with onset during the 4 days following administration of the study interventions, and all unsolicited AEs that occur during the 30 days following administration of the study interventions must be recorded into the appropriate section of the eCRF, irrespective of their intensity.

The time period for collecting and recording SAEs and pIMDs will begin at the first receipt of study interventions and will end 6 months after the last administration of the study interventions.

All AEs/SAEs leading to withdrawal from the study will be collected and recorded from the time of the first receipt of study intervention until the participant is discharged from the study. SAEs related to study participation or to a concurrent GSK medication/vaccine will be collected from the time consent is obtained until the participant is discharged from the study.

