- The number of days with solicited events ongoing beyond the 4-day follow-up period will be tabulated for each individual solicited event using descriptive statistics (mean, minimum, Q1, median, Q3, maximum). The same computations will be done for Grade 3 solicited events.

- The number and percentage of participants with any unsolicited AEs during the 30-day follow-up period (i.e. the day of vaccination and 29 subsequent days) with its exact 95% CI will be tabulated by group and by Medical Dictionary for Regulatory Activities (MedDRA) System Organ Class (SOC), High Level Term (HLT) and Preferred Term (PT). Similar tabulation will be done for Grade 3 unsolicited AEs, for any causally related unsolicited AEs, for Grade 3 causally related unsolicited AEs and for unsolicited AEs resulting in a medically attended visit. The verbatim reports of unsolicited AEs will be reviewed by a physician and the signs and symptoms will be coded according to the MedDRA Dictionary for Adverse Reaction Terminology. Every verbatim term will be matched with the appropriate Preferred Term. The above analysis by dose will also be performed.
- The number and percentage of participants with at least one report of SAE classified by the MedDRA Primary SOC, HLT and PTs and reported after vaccine administration (Day 1) up to study end (6 months after last vaccination) will be tabulated with exact 95% CI.
- The number and percentage of participants with at least one report of causally related SAE classified by the MedDRA Primary SOC, HLT and PTs and reported after vaccine administration (Day 1) up to study end (6 months after last vaccination) will be tabulated with exact 95% CI.
- The same tabulation will be presented for fatal SAEs.
- All SAEs will also be described in detail in a tabular listing.
- All pIMD will also be described in detail in a tabular listing.
- All AEs/SAEs leading to study/intervention discontinuation from dose 1 up to study end will be tabulated.
- The percentage of participants with at least one report of pIMD classified by the MedDRA SOC, HLT and Preferred Terms and reported after vaccine administration (Day 1) up to study end (6 months after last vaccination) will be tabulated with exact 95% CI.
- The percentage of participants with at least one report of related pIMD classified by the MedDRA SOC, HLT and Preferred Terms and reported after vaccine administration (Day 1) up to study end (6 months after last vaccination) will be tabulated with exact 95% CI.

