- The number and percentage of participants using concomitant medication (any medication and any antipyretic) during the 4-day and the 30-day follow-up period after each dose and overall will be tabulated with exact 95% CI.
- The number and percentage of participants using concomitant vaccination during the 30-day follow-up period after each dose and overall will be tabulated with exact 95% CI.
- Compliance in completing solicited events information will be tabulated after each dose and overall.

Some of the key safety analysis will be generated by age group at first vaccination (65-69 YOA, 70-79 YOA, \geq 70 YOA and \geq 80 YOA years) as mentioned below.

[figure not shown]
- The number and percentage of participants reporting each individual solicited administration site AE (any grade, Grade 3 and resulting in medically attended visit) and solicited systemic AE (any grade, Grade 3 and resulting in medically attended visit) during the 4-day follow-up period (i.e. the day of vaccination and 3 subsequent days) will be tabulated for each group after each dose and overall.

The number and percentage of participants with any unsolicited AEs during the 30-day follow-up period (i.e. the day of vaccination and 29 subsequent days) with its exact 95% CI will be tabulated by group and by MedDRA Primary SOC, HLT and PTs

- For clinicaltrials.gov and EudraCT posting purposes, percentage of participants of combined solicited and unsolicited non-serious adverse events during the 30-day follow-up period (i.e. the day of vaccination and 29 subsequent days) will be produced by System Organ Class and preferred terms and according to occurrence of each event.

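### Unsolicited non-serious AEs are collected over one 30-day window in Co-Ad and two in Control, and three SAP outputs (COVID-19 overall incidence, registry posting, unsolicited AEs by age group) state no by-dose or exposure-adjusted version

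*SAP*

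**What the plan says.** **Windows.** Under Protocol 4.1, Co-Ad receives both vaccines on Day 1. For Control: "Participants will receive a single dose of FLU vaccine at Visit 1 (Day 1), followed by a single dose of the RSV investigational vaccine" at Day 31. Protocol 10.3.7.1 requires that "all unsolicited AEs that occur during the 30 days following administration of the study interventions must be recorded". The schedules of activities in Protocol 1.3 follow this, recording unsolicited AEs at Visits 1 and 2 in Co-Ad and at Visits 1, 2 and 3 in Control. SAEs and pIMDs run continuously to 6 months after the last dose, and AEs leading to withdrawal run until discharge.

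**COVID-19.** The note to Protocol Table 12 (8.3.1) states that "COVID-19 cases will be collected during the same timeframes as those used for collecting and reporting the other safety information". Non-serious cases therefore follow the 30-day windows and serious cases follow the SAE period.

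**Outputs with a by-dose version.** In SAP 4.3.2, the any-AE table is given after each dose and overall. For the main unsolicited AE table the SAP adds: "The above analysis by dose will also be performed". The age-group table of solicited events is also by dose and overall.

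**Outputs with none stated.**
- The COVID-19 summary in SAP 4.5.1: "The overall incidence of COVID-19 AEs and SAEs, COVID-19 AEs leading to study intervention discontinuation", and further categories, identified by a standardized MedDRA query (SMQ).
- The registry-posting table in SAP 4.3.2: "percentage of participants of combined solicited and unsolicited non-serious adverse events during the 30-day follow-up period".
- The age-group table of unsolicited AEs in SAP 4.3.2, described as by group only.

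The SAP contains no person-time rate and no caution about unequal collection time. Its interpretive cautions, in 4.3.1.1 and 4.3.1.2, concern multiplicity.

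**The concern.** In study days 31 to 60, a new unsolicited non-serious event that is neither a pIMD nor a cause of withdrawal is collected in Control but not in Co-Ad. A per-participant percentage by group therefore covers about 30 days in one arm and 60 in the other, although the SAP describes the period as 30 days. With no true difference, Control shows more events, so the artefact favours co-administration. Comparing safety under the two schedules is a stated secondary objective, and the registry table is a public AE record of the trial. For COVID-19, if vaccination does not change its risk, any group contrast would reflect collection time.

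One row in SAP 4.5.1 has a related problem. Protocol 7.1 defines discontinuation of study intervention as not receiving all planned doses. Co-Ad participants have no later dose to miss, so COVID-19 AEs leading to discontinuation can in practice arise only in Control.

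**Working it through.** **Inputs from the documents.** Vaccination visits: 1 in Co-Ad, 2 in Control. Unsolicited AE window: 30 days per visit. Follow-up: about 180 days in Co-Ad (Visit 1 to contact) and about 30 + 180 = 210 in Control (Protocol Tables 3 and 4). Group size: 514.

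**The plan's own figure.** 462 evaluable with 10% not evaluable gives 462/0.90 = 513.3, rounded up to 514, as stated. It serves here only as a denominator.

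**Assumed inputs.** The documents give no safety event rate, so the risk p per 30-day window is an assumption, shown over a range.

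**Step 1: equal risk, independent windows.** Co-Ad shows p. Control shows 1 − (1 − p)². The ratio is 2 − p.

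| p per 30 days | Co-Ad | Control | Ratio | Expected participants of 514 |
|---|---|---|---|---|
| 2% | 2.0% | 3.96% | 1.98 | 10.3 vs 20.4 |
| 5% | 5.0% | 9.75% | 1.95 | 25.7 vs 50.1 |
| 15% | 15.0% | 27.75% | 1.85 | 77.1 vs 142.6 |
| 50% | 50.0% | 75.0% | 1.50 | 257.0 vs 385.5 |

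If someone tested these percentages at a two-sided 5% level, the chance of a nominally significant difference would be about 46% at p = 2% and 83% at p = 5%. The SAP plans no such test.

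**Step 2: within-person correlation ρ between windows.** Control shows 2p − [p² + ρp(1 − p)]. At p = 15%:
- ρ = 0.2: 0.30 − (0.0225 + 0.0255) = 0.252, ratio 1.68.
- ρ = 0.4: 0.30 − (0.0225 + 0.0510) = 0.2265, ratio 1.51.

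**Step 3: COVID-19 SAEs alone.** Collection is continuous, so for uncommon events the ratio is about 210/180 = 1.17. The allowed visit intervals give extremes of (30 + 180)/210 = 1.00 and (37 + 210)/180 = 1.37.

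**Step 4: combined COVID-19 AEs and SAEs.** Take a constant hazard h = 0.02/30 per day and a share f of serious cases. The cumulative hazard is h[30(1 − f) + 180f] in Co-Ad and h[60(1 − f) + 210f] in Control. Each percentage is 1 − exp(−cumulative hazard).
- f = 2%: hazards 0.022 and 0.042, ratio 1.89.
- f = 10%: hazards 0.030 and 0.050, ratio 1.65.
- f = 20%: hazards 0.040 and 0.060, ratio 1.49.

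**Step 5: after the fix.** One 30-day window against one 30-day window, or events per person-time, gives a ratio of 1.00 at equal risk.

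**The case against.** The strongest reply is that the main safety record already deals with this. The any-AE table and the main unsolicited AE table, with its Grade 3, related and medically attended versions, exist by dose. SAP 4.5.1 sends preferred-term incidence for COVID-19 to the standard summaries, so a 30-against-30-day comparison can be recovered at that level. The section also allows for a listing only, and neither it nor the registry bullet says the result will be one percentage per group. Safety is descriptive, and the confirmatory hypotheses concern immunogenicity alone.

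All of that stands, and it limits the point to three subsidiary outputs. It does not remove it. A participant with several COVID-19 preferred terms cannot be counted once by adding rows, so the SMQ-level total has no by-dose equivalent. The main by-dose table is not stated by age group. The registry table combines solicited and unsolicited events and cannot be rebuilt from it.

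A reader might infer that Control will look nearly twice as bad throughout. The documents do not support that:
- Solicited events are collected for 4 days after vaccination and chiefly follow the injections. Both groups receive the same two vaccines, so the background-time arithmetic does not apply to them in the registry table.
- pIMDs, SAEs and AEs leading to withdrawal are collected continuously in both groups. It would therefore be wrong to say that Co-Ad collects nothing in days 31 to 60.
- Only the unsolicited age-group table lacks a by-dose version; the solicited one has it.

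**Conclusion.** The point holds for three outputs: the COVID-19 SMQ-level overall incidence, the registry-posting table (its unsolicited part) and the unsolicited AE table by age group. Presented as one percentage per group, they would show a Control excess at equal background risk.

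A near-doubling, 1.98 to 1.85, is confined to uncommon non-serious unsolicited events. It rests on assumed risks of 2% to 15% per 30 days and on independent windows. The other results in the working are smaller, and the ratio of 1.49 to 1.89 for the combined COVID-19 count also depends on an assumed serious share of 20% to 2%. The direction does not depend on the chosen rate, but the size does.

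No confirmatory conclusion is affected and the main AE tables are sound in this respect. The change is worth making because the artefact runs one way and the SAP already has the convention that removes it.

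**What to change.** 1. In SAP 4.5.1, and in the registry-posting and age-group unsolicited AE items of 4.3.2, tabulate by dose as in the main unsolicited AE analysis: Co-Ad after Dose 1, Control after FLU, Control after RSV.
2. Use Days 1–30 after the first dose as the between-group row for non-serious COVID-19 AEs.
3. If a pooled Control column is kept, label it as two 30-day periods and put a person-time rate beside the percentage. Keeping it has some value: only the pooled column covers both vaccines in Control.
4. Report COVID-19 SAEs separately, with their own follow-up time (about 6 versus 7 months).
5. Add a note that COVID-19 AEs leading to discontinuation of study intervention can in practice occur only in Control.

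The data are already collected. The cost is SAP wording, a few extra columns and longer tables. Nothing changes in the primary analysis or in trial conduct.

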4.6. Other Analyses

Not Applicable.

4.7. Interim Analyses

There are no interim analyses planned for this study.

4.7.1. Sequence of analyses

A final analysis will be conducted once all the immunogenicity data (as clean as possible) are available for primary and secondary endpoints. This final analysis will include immunogenicity and safety data up to Visit 2 (Co-Ad group) or Visit 3 (Control group). Participants who undergo Visit 2 or Visit 3 assessments out of the allowed visit interval (refer to Table 3 and Table 4 of the protocol) will be excluded from the final analysis. The study conclusion on the primary objectives will be drawn based on this final analysis.

An end-of-study (EoS) analysis with all data including the safety data obtained until 6 months post-last dose will be performed. At the EoS analysis all statistical outputs will be re-generated and will be reported in an integrated Clinical Study Report.

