3. ANALYSIS SETS

Analysis Set	Definition / Criteria
Enrolled set*	Participants who agreed to participate in a clinical study after completion of the informed consent process.
Safety/Exposed set (ES)	All participants who received a study intervention. Analysis per group is based on the study intervention administered.
Per-Protocol set (PPS)	All eligible participants who received at least one study intervention as per-protocol in the control group and all study interventions in the Co-Ad group , had immunogenicity results pre-post-dose for at least one antigen, complied with blood draw intervals (refer to intervals mentioned below) and contribution of participants to PPS at specific timepoint will be defined by timepoint, without intercurrent medical conditions that may interfere with immunogenicity and without prohibited concomitant medication/vaccination.

*All participants enrolled and included in the database will be part of the enrolled set.

Intervals for the Co-Ad group: Visit1-Visit2=30-37 days

Intervals for the Control group: Visit1-Visit2=30-37 days, Visit2-Visit3=30-37 days

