3.1. Criteria for eliminating data from Analysis Sets

Elimination codes will be used to identify participants to be eliminated from analysis. Detail is provided below for each set.

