3.1.1. Elimination from Exposed Set (ES)

Code 1030 (Study intervention not administered at all), 800 (Fraudulent data) and code 900 (invalid informed consent) will be used for identifying participants eliminated from ES (see [Table 1](#)).

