3.1.2. Elimination from Per-protocol Set (PPS)

A participant will be excluded from the populations for analysis under the following conditions:

- For codes 800, 900, 1030, 1050 and 2020: participants will be eliminated for all visits.
- For codes 1070, 1080, 1090: participants will be eliminated from a specific visit (at which the condition is met) onwards as applicable for the respective group/antigens.
- For codes 1040, 2010, 2040, 2050, 2080: participants will be eliminated from a specific visit (at which the condition is met) onwards.
- 2090, 2100, 2120: participants will be eliminated at the specific visit at which the condition is met.

Table 1 List of elimination codes

Code	Condition under which the code is used	Visit /Contact(timepoints) where the code is checked	Visit from when it is applicable	Applicable for analysis set/endpoint
800	Fraudulent data	All	All	ES and PPS for analysis of immunogenicity
900	Invalid informed consent	All	All	ES and PPS for analysis of immunogenicity
1030	Study intervention not administered at all	All	All	ES and PPS for analysis of immunogenicity
1040	Administration of concomitant vaccine(s) forbidden in the protocol Use of any investigational or non-registered vaccine other than the study interventions during the period beginning 30 days before the first study vaccine administration or planned use during the study period. Planned or actual administration of a vaccine not foreseen by the study protocol in the period starting 30 days	Visit 1,2,3	From the specific visit the condition is met	PPS for analysis of immunogenicity

Code	Condition under which the code is used	Visit /Contact(timepoints) where the code is checked	Visit from when it is applicable	Applicable for analysis set/endpoint
	before the first study intervention administration and ending 30 days after the last study intervention administration. Note: In case an emergency mass vaccination for an unforeseen public health threat (e.g.: a pandemic) is recommended and/or organized by the public health authorities, outside the routine immunization program, the time period described above can be reduced if necessary for that vaccine provided it is used according to the local governmental recommendations and that the Sponsor is notified accordingly.			
1050	Randomisation failure: Subject not randomized in the correct group (To be attributed by Statistician only; Check SBIR, replacement, vaccine administration)	Visit 1	All	PPS for analysis of immunogenicity

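### SAP 4.7.1 excludes participants with an out-of-window Visit 2 or 3 from the whole final analysis, contradicting the SAP's own PPS-only, visit-specific elimination rules

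*SAP*

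**What the plan says.** SAP Section 4.7.1 sets the scope of the final analysis: "This final analysis will include immunogenicity and safety data up to Visit 2 (Co-Ad group) or Visit 3 (Control group"). The next sentence says that participants seen at Visit 2 or Visit 3 "out of the allowed visit interval (refer to Table 3 and Table 4 of the protocol) will be excluded from the final analysis". It names no analysis set, endpoint or visit, and it is mandatory. The section adds: "The study conclusion on the primary objectives will be drawn based on this final analysis". For the end of study it says: "At the EoS analysis all statistical outputs will be re-generated and will be reported in an integrated Clinical Study Report".

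The rest of the SAP deals with window violations differently:

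- Section 3.1: "Elimination codes will be used to identify participants to be eliminated from analysis".
- Section 3, PPS definition: "contribution of participants to PPS at specific timepoint will be defined by timepoint".
- Section 3.1.1, on the ES: "Code 1030 (Study intervention not administered at all), 800 (Fraudulent data) and code 900 (invalid informed consent) will be used". No visit-window code is listed.
- Section 3.1.2: "2090, 2100, 2120: participants will be eliminated at the specific visit at which the condition is met". Code 2090 is the blood-sample window, 30-37 days.
- Table 1: code 2080 (Control dose interval outside 30-37 days) takes effect at Visit 3. Codes 2080 and 2090 both apply only to the PPS for immunogenicity.
- Section 4.3.2 analyses safety on the ES. Section 4.2 adds an ES immunogenicity analysis when 5% or more of vaccinated participants with serology are excluded from the PPS in any group.

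Protocol Section 9.5.1 has the parallel sentence to 4.7.1, but with permissive wording (may, not will).

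**The concern.** The two sets of rules assign the same participant to different analyses. Three consequences follow if 4.7.1 is applied as written.

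1. **Primary HI comparisons.** A Control participant with an in-window Day 31 sample and a late Visit 3 has valid HI data. Table 1 keeps them and 4.7.1 drops them. Only Control has a Visit 3, so only Control can lose HI data this way. The four HI comparisons are in the 1st sequence, which gates the RSV-B test.
2. **The supporting ES analysis.** It is meant to complement the PPS by bringing excluded participants back. Under 4.7.1 it would lack those excluded for window violations.
3. **Safety.** Exposed participants would be missing from the final-analysis safety tables until the EoS outputs are produced.

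The trial is open-label, so membership of the confirmatory analysis should not depend on which SAP section the programmer follows.

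**Working it through.** **Comparing the rules case by case**

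| Case | SAP Table 1 | SAP 4.7.1 read literally |
|---|---|---|
| Co-Ad, Visit 2 out of window | Out of PPS at Visit 2 (2090); stays in ES and safety | Out of everything, including safety |
| Control, Visit 2 and RSV dose out of window | Out of PPS at Visit 2 (2090) and Visit 3 (2080); stays in ES and safety | Out of everything, including safety |
| Control, Visit 2 in window, Visit 3 on day 38 after Visit 2 | Out of PPS at Visit 3 only (2090); Day 31 HI kept; stays in ES and safety | Out of everything, including Day 31 HI and safety |
| Control, vaccinated at Visit 2, never attends Visit 3 | Code 2100 at Visit 3 only; Day 31 HI kept; stays in ES and safety | Not caught, as there is no out-of-window assessment; Day 31 HI kept |

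The PPS for immunogenicity differs only in the third row. Safety and the ES differ in the first three. The last two rows also show that, under 4.7.1, returning one day late costs a participant's HI data while not returning at all does not.

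**Reproducing the planned power (SAP Section 5, Table 2)**

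Inputs: one-sided alpha 0.025; margin log10(1.5) = 0.1761; true difference log10(1.05) = 0.0212; SD 0.6 per FLU strain and 0.45 for each RSV endpoint; 462 evaluable per group.

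- Distance to the margin: 0.1761 − 0.0212 = 0.1549.
- FLU: SE = 0.6 × √(1/462 + 1/462) = 0.03948; noncentrality 0.1549/0.03948 = 3.92; power from the noncentral t with 922 df = 97.50% (plan: 97.5%).
- RSV: SE = 0.45 × √(2/462) = 0.02961; noncentrality 5.23; power 99.95% (plan: 99.9%).
- Global power = 100% minus the summed type II errors = 100 − (4 × 2.50 + 2 × 0.05) = 89.9% (plan: about 90%).

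**Effect of the two rules on the HI comparisons**

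Non-evaluable per group: 514 − 462 = 52, or 10.1%. The protocol glossary defines evaluable as included in the per-protocol analysis, so 462 is already net of window exclusions. The documents give no out-of-window rate. Assume that k of the 52 non-evaluable Control participants missed only the Visit 3 window. Table 1 then keeps 462 + k Control participants for Day 31 HI, while 4.7.1 returns the number to 462. Co-Ad stays at 462. RSV power is the same under both rules, because code 2090 removes the Visit 3 RSV result either way.

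| k (assumed) | Control n for HI, Table 1 | Power per strain | Global power, Table 1 | Global power, 4.7.1 |
|---|---|---|---|---|
| 10 | 472 | 97.62% | 90.37% | 89.89% |
| 26 | 488 | 97.80% | 91.07% | 89.89% |
| 52 (upper bound) | 514 | 98.05% | 92.07% | 89.89% |

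The largest difference is 92.07 − 89.89 = 2.18 points, all of it above plan.

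**Effect on safety**

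At assumed out-of-window rates of 2%, 5% or 10%, about 10, 26 or 51 of 514 vaccinated participants per group would leave the final-analysis safety tables under 4.7.1 (514 × 0.02, 0.05, 0.10). Under Table 1 none would.

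**The case against.** The strongest reply is that the operative rules are already complete. Eliminations are made by code, the codes give set and visit, and safety is assigned to the ES. Section 4.7.1 sits under a heading about the sequence of analyses, and no code exists that would carry out the literal exclusion. SAP Section 4.8 declares no change from the protocol, whose own sentence only says that such participants may be excluded. On this view 4.7.1 is a loose restatement and nobody would program it literally. The consequences are also small: power stays at plan, the 2.2-point maximum needs every non-evaluable Control participant to have failed for the same single reason, and EoS re-generates all outputs.

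Most of this is right about intent and size. It does not remove the conflict. The sentence is mandatory, follows directly on a definition that includes safety, and governs the analysis from which the primary conclusion is drawn. The appeal to the protocol also cuts the other way: the SAP turns a permissive statement into a mandatory one while declaring no change.

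A further point concerns Protocol Section 8, which leaves the PPS impact of special circumstances, including the 30-day extension of the Control Visit 2 interval, to case-by-case decision, whereas code 2080 is a fixed limit. That difference is real but separate. For the present point, Section 8 shows only that the protocol too treats timing departures as a PPS question.

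**Conclusion.** The concern holds. As written, SAP 4.7.1 states a broader exclusion than SAP Sections 3 to 3.1.2 and Table 1, and the two cannot both be followed. It should be corrected, although PPS-only elimination is very probably what was meant.

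There is no loss against planned power and no direction of bias is claimed. The cost of following 4.7.1 is at most about 2.2 points of global power above plan, on the assumption that all 52 non-evaluable Control participants missed only the Visit 3 window; with 10 such participants it is about 0.5 points. The safety gap would last until EoS. What matters is that the Control set for four gating primary comparisons, and the content of the ES analysis, depend on which section is followed.

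**What to change.** In SAP Section 4.7.1, replace the exclusion sentence with:

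> Participants with out-of-window visits are eliminated from the PPS for immunogenicity as specified in Table 1 (code 2090: at the affected visit; code 2080: Visit 3 in the Control group). They remain in the ES for all safety and ES immunogenicity analyses.

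The permissive wording in Protocol Section 9.5.1 is compatible with this and can be aligned at the next amendment.

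Cost: one SAP sentence. It needs no protocol amendment, new data, change in sample size or new elimination code, because the text only points to rules already in Table 1.
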